10.8.1 EXPOSURE TO STUDY TREATMENT

The number of doses received, actual dose received in mg, the total planned dose in mg/kg and the extent of exposure, (calculated as last dose date - first dose date +1), will be summarized using descriptive statistics by cohort, study part and overall.

A by-patient listing with the treatment administration data will be also presented and reasons for doses missed will be also listed.

10.8.2 LABORATORY DATA

Tables by visit and by NCI CTC grades (grade 0, grade 1, grade 2, grade 3, grade 4, grade 5) will be presented by laboratory test, where applicable. Worst-post baseline NCI CTC grade for applicable laboratory tests will be also summarized.

Urinalysis results (normal/ abnormal – low/ abnormal - high) will be summarized by visit.

Data listings will be produced for all collected laboratory data, including pregnancy test results.

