7.1 Inclusion and Exclusion Criteria

7.1.1 Inclusion Criteria

Patients must meet all of the following criteria in order to be included in the study:

- 1. Male or female patients, 18 years of age or older at the time of consent.
- 2. Provide written informed consent prior to performing any study-related procedure.
- 3. Histologically or cytologically confirmed patients with advanced or metastatic solid tumors will be enrolled, for both Dose Escalation and Expansion.
- 4. Patients must have been treated with established standard-of-care therapy, or physicians have determined that such established therapy is not sufficiently efficacious, or patients have declined to receive standard-of-care therapy.
- 5. Measurable disease (i.e., at least one measurable lesion per RECIST, version 1.1) (Eisenhauer, et al., 2009).
- 6. Eastern Cooperative Oncology Group (ECOG) performance status of 0 or 1 (Oken, et al., 1982).

- 7. Adequate organ function defined as:
 - a. Hepatic:
 - Serum alanine aminotransferase (ALT) ≤3 × upper limit of normal (ULN), ≤5 × ULN in the presence of liver metastases
 - Serum aspartate aminotransferase (AST) $\leq 3 \times ULN$, $\leq 5 \times ULN$ in presence of liver metastases
 - Serum bilirubin $\leq 1.5 \times ULN$ (unless due to Gilbert's syndrome or hemolysis)
 - b. Renal:
 - Creatinine clearance >30 mL/minute using Cockcroft Gault equation
 - c. Hematologic:
 - Absolute neutrophil count $\geq 1000/\mu L$
 - Platelets \geq 75,000/µL
 - Hemoglobin $\geq 8 \text{ g/dL}$
- 8. Patient is willing and able to comply with all protocol-required assessments, visits, and procedures, including a pretreatment tumor biopsy. Archival tumor biopsies (slides or FFPE tissue block) are acceptable at baseline.

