7.1.2 Exclusion Criteria

Patients meeting any of the following criteria are ineligible to participate in this study:

- 1. Less than 3 weeks, from prior cytotoxic chemotherapy or radiation therapy; and less than 5 half-lives or 3 weeks from biological therapies, whichever is shorter, prior to the first dose of OBI-888.
- 2. Has undergone a major surgical procedure (as defined by the Investigator) or significant traumatic injury within 28 days prior to the first dose of OBI-888.
- 3. Presence of an active autoimmune or inflammatory disease requiring systemic treatment

within the past 2 months or a documented history of clinically severe autoimmune disease that requires systemic steroids or other immunosuppressive medications. Local steroid injections, intermittent use of topical, inhaled, ophthalmologic, intra-articular, topical, or intranasal corticosteroids, or systemic corticosteroids at physiologic doses not to exceed 10 mg/day of prednisone or equivalent would not be excluded from the study.

- 4. Presence of primary immunodeficiency or receiving systemic steroids of >10 mg/day prednisone or equivalent or other immunosuppressive agents within 14 days prior to the first dose of OBI-888.
- 5. Has active bacterial, viral, fungal, or mycobacterial infection requiring systemic therapy, including known infection with human immunodeficiency virus (HIV) or active infection with hepatitis B virus or hepatitis C virus. Patients with HIV infection are eligible if CD4+ T-cell counts are ≥350 cells/µL; patients on antiretroviral therapy should be on an established dose for at least 4 weeks and have an HIV viral load less than 400 copies/mL prior to enrollment.
- 6. Patients with a history of solid organ transplant.
- 7. Unresolved toxicities from prior anticancer therapy, defined as having not resolved to Grade 0 or 1 (using NCI CTCAE version 4.03), except for alopecia and laboratory values listed in the inclusion criteria.
- 8. Receipt of any prior therapy targeting Globo H.
- 9. Known hypersensitivity to OBI-888 or its excipients.
- 10. Has known untreated central nervous system metastases. Patients with treated brain metastases are eligible if there is no evidence of progression for at least 4 weeks after central nervous system-directed treatment, as ascertained by clinical examination and brain imaging (magnetic resonance imaging [MRI] or computed tomography [CT]) during the screening period.

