14.5 Safety Analysis

AEs will be coded according to Medical Dictionary for Regulatory Activities (MedDRA) version 19.0 or higher and assessed for severity using CTCAE version 4.03. AEs will be summarized by system organ class and preferred term and presented in decreasing order of incidence. DLTs will also be summarized by dose and cohort. The incidence of TEAEs (events with onset dates on or after the start of the study drug) will be included in incidence tables. Events with missing onset dates will be included as treatment-emergent. If a patient experiences more than 1 occurrence of the same AE, the occurrence with the greatest severity and the closest association with the study drug will be used in the summary tables. SAEs and AEs causing discontinuation will be tabulated. All AEs will be listed by patient, along with information regarding onset, duration, relationship and severity to study drug, action taken with study drug, treatment of event, and outcome.

Vital signs, ECG data, hematology, serum chemistry, coagulation, and urinalysis parameters from baseline and during study will be examined. Treatment emergent changes in key laboratory parameters will be identified. Clinical laboratory data and vital signs will be summarized for each time point evaluated using descriptive statistics including mean values and mean change from baseline values, as well as numbers of patients with values outside limits of the normal range at each time point.

Summary tables will be provided for concomitant medications initiated prior to study enrollment or during the study period.

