8. ANALYSIS ENDPOINTS

Analysis endpoints are listed as per protocol. Only those endpoints marked with * will be analyzed in the aCSR. Exploratory analyses are to be conducted by OBI Translational Biology (or their designee) and may be included as appendices in the aCSR.

8.1 PRIMARY ENDPOINTS:

- DLTs with OBI-888*.
- AEs/ serious AEs (SAEs) and laboratory abnormalities as graded by National Cancer Institute Common Terminology Criteria for Adverse Events (NCI CTCAE) version 4.03*.
- MTD and RP2D of OBI-888.

8.2 SECONDARY ENDPOINTS:

- Percentage of patients with ORR, CBR*, DOR and PFS according to Response Evaluation Criteria in Solid Tumors version 1.1 (RECIST 1.1).
- Percentage of patients with anti-OBI-888 ADAs in blood*.
- PK and PD parameters of OBI-888*.

8.3 EXPLORATORY ENDPOINTS:

- Globo H and related glycan expression in tumor tissue by IHC.
- ADCC and CDC.
- Identify potential predictive markers by IHC or molecular analysis.
- Tumor Infiltrating Lymphocytes (TILs) including natural killer (NK) cells, and programmed death ligand 1 (PD-L1) expression in tumor tissue samples by IHC.
- Killer cell immunoglobulin-like receptor (KIR), human leukocyte antigen (HLA), and Fc receptor gamma genotype.
- Glycan analysis of OBI-888.

Review Status: Final Version: 2.0 Version Date: 02JUN2022

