11. DEVIATIONS FROM ANALYSIS AS DESCRIBED IN THE PROTOCOL

The Sponsor elected to generate an aCSR focusing on safety and exposure. As a result, the following analyses will not be conducted: DOR, best overall response (BOR), PFS, ORR. Protocol deviations will not be summarized nor listed. Medical history, current medical conditions, prior and concomitant medications, prior anticancer therapy, and smoking history will be summarized in the listings only. Serious TEAEs and SAEs leading to discontinuation of OBI-888 will not be summarized. Shift tables of the worst on study laboratory toxicity based on NCI CTCAE grading will not be presented; summaries of laboratory data (with exception of summary described in section 10.8.2), and ECOG over time will not be presented.

DLT criteria as collected on eCRF will be analysed.

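### No planned laboratory summary links a patient's baseline grade to that patient's worst grade, so the worst-grade table mixes pre-existing with new or worsened abnormalities

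*SAP*

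**What the plan says.** **The endpoint.** SAP 8.1 lists "AEs/ serious AEs (SAEs) and laboratory abnormalities as graded by National Cancer Institute" and the rest of that item as a primary endpoint. It carries the asterisk that marks what the abbreviated report will analyse. SAP 10.7.1 B takes this endpoint as its title but specifies only adverse event analyses. The laboratory grades are handled in SAP 10.8.2.

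**The tables.** SAP 10.8.2 plans "Tables by visit and by NCI CTC grades" for each applicable test, and then "Worst-post baseline NCI CTC grade for applicable laboratory tests will be also summarized". It also plans listings of all collected laboratory data.

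**What is dropped.** SAP 11 states: "Shift tables of the worst on study laboratory toxicity based on NCI CTCAE grading will not be presented". It adds: "summaries of laboratory data (with exception of summary described in section 10.8.2), and ECOG over time will not be presented".

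**What the protocol planned.** Protocol 14.5 says: "Treatment emergent changes in key laboratory parameters will be identified". It also plans mean change from baseline for laboratory data.

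**Who may enter.** Exclusion 7 in Protocol 7.1.2 requires toxicity from earlier anticancer treatment to have settled to Grade 0 or 1, "except for alopecia and laboratory values listed in the inclusion criteria". The limits in Protocol 7.1.1 include ALT and AST "≤5 × ULN in the presence of liver metastases", haemoglobin from 8 g/dL, neutrophils from 1000/µL, platelets from 75,000/µL and creatinine clearance above 30 mL/min.

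**The concern.** The study has no control arm, so the only reference for a laboratory abnormality on OBI-888 is the patient's own baseline. The SAP uses that reference elsewhere. A TEAE must start on or after first dose or worsen from its earlier state (SAP 10.7.1 B), and vital signs are shown as changes from baseline (SAP 10.8.3). Laboratory grades, although part of a primary endpoint, get neither treatment.

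In the worst-grade table, a patient who enters with an abnormal value and stays there is counted in the same cell as one who was normal and became abnormal on treatment. At stake is how the laboratory part of the endpoint is read by dose level and by cohort. Groups are small: 14 patients over three dose levels in Part A, and up to 9 per cohort in the first stage of Part B. One unchanged entry abnormality moves a nine-patient cohort by 1/9, or 11 percentage points.

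**Working it through.** The plan states no figure on this point, so the check is first textual. Two short calculations follow, both on assumed inputs.

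**1. Can patients enter with graded abnormalities?** The exemption in Exclusion 7 has an effect only if some of the exempted values may lie above Grade 1. This does not depend on knowing which limit corresponds to which grade. Tests without an entry limit, such as ALP, albumin and electrolytes in Protocol Table 12-1, are restricted by Exclusion 7 only when the abnormality is left over from prior therapy.

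**2. Does any planned laboratory summary link baseline to worst grade?** The by-visit table gives group counts at each visit. The worst-grade table gives one count per grade. Shift tables and the other laboratory summaries are dropped. No laboratory summary contains the link.

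**3. Can the link be recovered from the two tables together?** Let n be the cohort size, k the number at Grade 2 or above at baseline, and m the number whose worst post-baseline grade is 2 or above. The number who moved from below Grade 2 to Grade 2 or above lies between max(0, m − k) and min(m, n − k). With assumed values n = 9, k = 3, m = 3:

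- Lower bound: max(0, 3 − 3) = 0. The same three patients are abnormal throughout.
- Upper bound: min(3, 9 − 3) = 3. Three new patients become abnormal, and the original three fall below Grade 2 at every later visit.

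The first case is 3/9 = 33% in the worst-grade table with 0/9 newly abnormal. The second gives the same table with 3/9 newly abnormal. The second is less likely, but group counts cannot exclude it or anything in between.

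**4. How much of the count could be pre-existing?** Let b be the share at Grade 2 or above at baseline who are still so at one or more later samples, and w the rate of new Grade 2 or above among the others. Neither is in the documents; the assumed ranges are b = 5% to 30% and w = 0% to 10%. Then

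- share shown in the table = b + (1 − b)w
- newly abnormal share = (1 − b)w
- pre-existing part of the count = b / [b + (1 − b)w]

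| b | w | Shown | Newly abnormal | Pre-existing part |
|---|---|---|---|---|
| 5% | 10% | 14.5% | 9.5% | 34% |
| 10% | 5% | 14.5% | 4.5% | 69% |
| 20% | 5% | 24.0% | 4.0% | 83% |
| any | 0% | b | 0% | 100% |

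Over the assumed ranges the pre-existing part runs from 34% to 100%. The expected number of such patients per test is 14 × 0.05 = 0.7 to 14 × 0.30 = 4.2 among the 14 in Part A, and 30 × 0.05 = 1.5 to 30 × 0.30 = 9.0 in a full Part B cohort of 30. The formula treats a patient who goes from Grade 2 to a higher grade as pre-existing, so it does not count that worsening.

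**The case against.** Much of the case for leaving the plan as it is stands.

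- **Label.** A reader might infer that the SAP counts entry abnormalities as drug toxicity. It does not. The table is described as worst post-baseline grade, not as treatment-emergent or related. The risk lies in how it is read.
- **Baseline is visible.** A reader might infer that baseline is ignored altogether. The by-visit tables follow eCRF visits (SAP 10.2), so they presumably show pre-dose grades, and the listings allow a patient-by-patient comparison. That work is left to the reader, test by test.
- **TEAE route.** A reader might infer that no table identifies treatment-emergent laboratory changes. Protocol 12.4 makes any result that the investigator judges clinically significant an adverse event. Such events reach TEAE tables that take account of the pre-dose state. What is left out is graded change not reported as an adverse event; the endpoint names laboratory abnormalities alongside adverse events.
- **Declared scope.** SAP 11 states the omission openly as a result of the abbreviated report. Protocol 14 lets the SAP prevail where the two differ, and the synopsis leaves laboratory change from baseline to the SAP. Protocol 14.5 does not call for a shift table. So this is not a breach of the protocol.
- **No decision depends on it.** DLTs are analysed as collected on the eCRF, the RP2D was settled at safety committee review, and the Simon rule uses objective responses.
- **Cohort comparisons.** It is tempting to say that cohorts with more liver metastases will look more toxic. The documents give no metastasis or laboratory data by cohort, so this is only a possibility.

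None of this supplies the missing link within patients. A declared omission still leaves a table that cannot separate entry status from worsening.

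**Conclusion.** The point holds as a limited gap in reporting. The planned worst-grade table combines abnormalities already present at entry with new or worsened ones, and no other laboratory summary separates them. The gap covers graded laboratory changes that were not reported as adverse events.

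Its size is not known from the documents. The 3/9 against 0/9 example and the 34% to 100% range rest on assumed rates. Any matching of an entry limit to a particular CTCAE grade is also an assumption, because the documents do not reproduce the cut-offs. The conclusion itself needs only the exemption in Exclusion 7, the two tables in SAP 10.8.2 and the exclusions in SAP 11. It does not affect the DLT, RP2D or response decisions.

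**What to change.** In SAP 10.8.2, present worst post-baseline grade cross-tabulated by baseline grade for each gradable test, by dose level in Part A and by cohort in Part B. Take baseline as defined in SAP 10.2. Add a count of patients whose worst grade exceeds their baseline grade. Amend the shift-table sentence in SAP 11 to match.

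The margins of this table keep the worst-grade counts already planned. It needs no new data, visits or patients, because the grades are required for the by-visit table and baseline is already defined. The cost is SAP wording, one larger table than the abbreviated report planned, and a partial reversal of the sponsor's decision on its scope.

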10.8.3 VITAL SIGNS

Vital signs assessments (temperature, pulse, systolic and diastolic blood pressure) and weight will be tabulated by visit (results and changes from baseline).

Data listings will be produced for all collected vital signs data.

10.8.4 ELECTROCARDIOGRAM

Data listings for electrocardiogram (ECG) data will be produced.

10.8.5 OTHER SAFETY PARAMETERS

ECOG will not be summarized.

Physical examination results (normal/abnormal-not clinically significant/abnormal-clinically

Review Status: Final Version: 2.0 Version Date: 02JUN2022

significant) will be summarized by visit and listed.

11. DEVIATIONS FROM ANALYSIS AS DESCRIBED IN THE PROTOCOL

The Sponsor elected to generate an aCSR focusing on safety and exposure. As a result, the following analyses will not be conducted: DOR, best overall response (BOR), PFS, ORR. Protocol deviations will not be summarized nor listed. Medical history, current medical conditions, prior and concomitant medications, prior anticancer therapy, and smoking history will be summarized in the listings only. Serious TEAEs and SAEs leading to discontinuation of OBI-888 will not be summarized. Shift tables of the worst on study laboratory toxicity based on NCI CTCAE grading will not be presented; summaries of laboratory data (with exception of summary described in section 10.8.2), and ECOG over time will not be presented.

DLT criteria as collected on eCRF will be analysed.

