3. INTRODUCTION

This Statistical Analysis Plan (SAP) covers the statistical analysis and reporting for the protocol OBI-888-001 final version 5.0 (dated 08 May 2020), and electronic case report form (eCRF) production version 5.4 dated 17 Nov 2020.

The Sponsor elected to generate an abbreviated Clinical Study Report (aCSR) focusing on safety and exposure.

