10.7.1 PRIMARY ENDPOINTS

A. DLTs with OBI-888

The period for DLT is 28 days from the start of first dose of Investigational Product at Day 1 in study part A.

A DLT is defined as the occurrence of any of the following events within the first cycle of treatment and are considered to be at least possibly related to OBI-888:

- Grade 4 neutropenia
- Grade ≥ 3 febrile neutropenia with or without infection
- Grade 4 thrombocytopenia
- Grade ≥ 3 nausea and vomiting or diarrhea for more than 72 hours despite optimal supportive care
- Any Grade ≥ 3 non-hematological AE, except for nausea, vomiting, or diarrhea that does not resolve before the next infusion
- Grade 4 infusion reactions, and Grade ≥ 3 infusion reactions that recur despite decreasing infusion rate and optimal supportive care measures

DLTs will be displayed by assigned dose and cohort in a frequency table in decreasing order of incidence. DLTs will not be programmatically derived but analyzed as collected on the eCRF.

AE terms will be coded using the most current version of the Medical Dictionary for Regulatory Activities (MedDRA). AEs will be graded according to the NCI CTCAE version 4.03. All AEs unless they have been determined to be not related to study drug will be taken into consideration in determining DLTs.

B. AEs/SAEs and laboratory abnormalities as graded by NCI CTCAE version 4.03

A treatment-emergent adverse event (TEAE) is defined as an AE with onset dates on or after the start of study drug or if it is present prior to receipt of the study treatment but worsens in severity or increases in frequency on or after the first dose. AEs having both onset and end dates missing will be considered as TEAEs.

Events reported as "Unrelated" or "Unlikely related" to study drug will be considered as unrelated to the study drug. Events reported as "Possibly related", "Probably related", "Definitely related" to study drug or without relationship information will be considered as related to the treatment.

Tables will display the incidence of events (number of events, number of patients with any event, number of patients with any event in each specific system organ class [SOC], and number of patients with any event for each specific preferred term [PT]).

For each AE, only the highest grade and closest association with study drug by patient will be considered in the incidence analyses.

The following tables will be produced:

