Tables by SOC and PT will be displayed for following AEs. Only those AEs marked with * will be

Review Status: Final Version: 2.0 Version Date: 02JUN2022

analyzed in the aCSR:

- DLTs
- Treatment-emergent adverse events (TEAEs)*
- TEAEs grade ≥ 3*
- TEAEs related to OBI-888*
- TEAEs leading to discontinuation of OBI-888*
- Serious TEAEs
- Serious TEAEs related to OBI-888*
- AEs leading to discontinuation of OBI-888
- SAEs leading to discontinuation of OBI-888
- TEAEs leading to death*

A table of TEAEs by SOC, PT and worst CTCAE grade (per summarization level) will be presented.

The following listings will be prepared:

- · All AEs, with DLTs flagged
- All SAEs
- AEs related to OBI-888
- AEs grade ≥ 3
- All TEAEs leading to OBI-888 discontinuation
- AEs leading to death
 - C. MTD and RP2D of OBI-888

The MTD and RP2D were identified as 20 mg/kg during SRC review.

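### SAEs of any causality belong to a starred primary endpoint, but the only table the SAP plans that selects on seriousness is limited to related events

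*SAP*

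**What the plan says.** SAP Section 3 sets the scope: "The Sponsor elected to generate an abbreviated Clinical Study Report (aCSR) focusing on safety and exposure". Section 8 gives the rule for endpoints, "Only those endpoints marked with * will be analyzed in the aCSR", and 8.1 puts a star on the primary endpoint "AEs/ serious AEs (SAEs) and laboratory abnormalities as graded by National Cancer Institute Common Terminology Criteria for Adverse Events (NCI CTCAE) version 4.03". That bullet carries no restriction by causality.

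Section 10.7.1 uses the same star convention for its AE tables by SOC and PT. Serious TEAEs is listed without a star. The next entry, "Serious TEAEs related to OBI-888", has one. "SAEs leading to discontinuation of OBI-888" is a separate entry, also without a star. The same section defines relatedness: events reported as unrelated or unlikely related "will be considered as unrelated to the study drug", while events reported as possibly, probably or definitely related "to study drug or without relationship information will be considered as related to the treatment". A listing of all SAEs is kept.

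Section 11, which declares departures from the protocol, states "Serious TEAEs and SAEs leading to discontinuation of OBI-888 will not be summarized". Protocol 14.5 had planned to tabulate SAEs, with no causality limit.

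**The concern.** The SAP says a primary endpoint that includes SAEs will be analysed, and then removes the table that would give its overall incidence. What remains is the subset attributed to the drug. In an open-label study with no control arm, attribution is an unblinded judgement with nothing to compare it with, so the all-causality count is the figure that does not depend on that judgement. The pattern is also uneven. For TEAEs as a whole both the all-causality and the related tables are kept, and the discontinuation and death tables are all-causality. Only seriousness is cut back to related events. A reader who goes to the one table labelled serious could see few or no patients when a sizeable share had an SAE.

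**Working it through.** The plan states no figure to reproduce. The check sets the specified outputs side by side and then uses the trial's own early counts as an illustration.

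**1. What each specified AE table shows (SAP 10.7.1)**

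| Table | Causality | Selects on seriousness? |
|---|---|---|
| TEAEs* | any | no |
| TEAEs grade ≥ 3* | any | no |
| TEAEs related* | related | no |
| TEAEs leading to discontinuation* | any | no |
| Serious TEAEs related* | related | yes |
| TEAEs leading to death* | any | selects on outcome; every event is serious, because fatal is a criterion in Protocol 12.5.2 |
| TEAEs by worst CTCAE grade | any | no, but Grades 4 and 5 are visible; Protocol Table 12-2 labels them life-threatening and death, both seriousness criteria in 12.5.2 |
| Serious TEAEs (no star) | any | yes, but not produced |

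Section 10.7.1 describes the content of these tables as events and patients by SOC and PT, with no split by seriousness. A non-fatal SAE of Grade 3 or lower therefore cannot be recognised as serious in any all-causality table.

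**2. Does a missing star mean no summary?** Not by itself. DLTs also lack a star in that list, yet part A of 10.7.1 gives them their own frequency table. Serious TEAEs have no such sentence anywhere in the SAP.

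**3. Reading Section 11.** Taken alone, the sentence could mean only serious events that led to discontinuation. Section 10.7.1 lists Serious TEAEs and SAEs leading to discontinuation as two separate items, both unstarred, so the sentence is read as naming both. On the narrower reading the Serious TEAEs table would still be unstarred, with no other text providing it.

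**4. Illustration from Protocol 4.3.1 (March 2020)**

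Inputs: 17 enrolled = 14 in Part A + 3 in Part B; 8 SAEs in 5 patients, from all three dose cohorts; all assessed as unrelated; two Grade 5 events in one patient, the rest Grade 3. Assumptions: all 17 were dosed and all 8 SAEs were treatment-emergent.

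- SAP 10.1 reports Parts A and B separately, so the count has to be placed by part. The 5 and 10 mg/kg levels exist only in Part A, so at least 1 + 1 = 2 of the 5 patients were in Part A. Part B had 3 patients, which gives the same bound: 5 − 3 = 2. At most, all 5 were in Part A.
- All-causality Part A total: 2/14 = 14.3% to 5/14 = 35.7%. If the three dose cohorts mean Part A cohorts only, the lower bound becomes 3/14 = 21.4%, inside that range.
- Related-only Part A total: 0/14. Every SAE had a recorded assessment of unrelated, so the rule that counts missing relationship as related adds none.
- Exact (Clopper-Pearson) 95% intervals, with lower limit Beta(0.025; x, n−x+1) and upper limit Beta(0.975; x+1, n−x): 2/14 gives 1.8% to 42.8%, 5/14 gives 12.8% to 64.9%, and 0/14 has an upper limit of 23.2%. The SAP plans no interval for AE incidence; these only show how imprecise the counts are.
- By grade: 8 − 2 = 6 Grade 3 SAEs. These would sit in the grade ≥ 3 table among non-serious events. The two Grade 5 events would show in the worst-grade table and, if recorded as leading to death, in the death table.

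The documents do not give the number of SAE patients per dose level, so the split by dose cannot be shown.

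**The case against.** The strongest reply is that this is a deliberate and declared scope cut. The revision history says stars were added in 10.7.1 because the abbreviated report would not carry every AE analysis of SAP version 1.0. Section 11 repeats the cut, and Protocol Section 14 lets the SAP prevail. The star in 8.1 sits on a composite bullet and does not in terms promise an SAE table. Every SAE is listed by patient, and in a study this small the count can be made by hand.

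Much of this stands. There is no concealed deviation, and SAP precedence settles the difference from Protocol 14.5. It does not settle the mismatch between SAP 8.1 and SAP 10.7.1 with Section 11, because both sides are in the same document. A listing gives no incidence by dose or cohort.

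A reader might infer three stronger things that the documents do not support:

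- *That no all-causality SAE incidence is planned at all.* The death table is all-causality and every event in it is serious, and the worst-grade table shows Grade 4 and 5 events. The gap is in SAEs overall and in non-fatal SAEs.
- *That unrelated SAEs drop out of the report.* They remain in the SAE listing and are counted, though not marked as serious, in the general TEAE tables.
- *That the report would show 0/17 against a true 5/17 (29.4%).* SAP 10.1 has no column pooling Parts A and B, so neither figure would appear. The Part A range is the one that matches the layout.

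The table shells are in a separate document (SAP Section 12) that was not available. A shell for all serious TEAEs would contradict Section 11 as read here, so the SAP text would still need correcting.

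**Conclusion.** The point holds for the SAP text. A starred primary endpoint includes SAEs of any causality, but the SAP specifies no all-causality incidence of SAEs overall, or of non-fatal SAEs, by dose or cohort. This rests on reading Section 11 together with the two separate entries in 10.7.1, and on the absence of any other sentence that provides the table.

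On the March 2020 snapshot, and under the two assumptions stated with the illustration, the cut would turn a Part A total of 14.3% to 35.7% into zero in the one table selected by seriousness, and six of the eight SAEs would not be identifiable as serious in any all-causality table. Those data are more than two years older than SAP version 2.0 and later counts are not in the documents, so the size in the final report is unknown. This is a gap in the specified summary, not a loss of data. It is worth correcting because the report is about safety.

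**What to change.** In SAP 10.7.1, star Serious TEAEs and produce the SOC and PT table regardless of causality, with patients and events, beside the related table. Use the layout of 10.1: by dose with a total for Part A, by cohort with a total for Part B. In Section 11, limit the exclusion to SAEs leading to discontinuation of OBI-888.

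The cost is one standard table from data already collected and listed, a version update to a SAP now marked final, and a matching shell in the mock-up document if none exists. Nothing in study conduct or patient management changes.
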